8.1.2 Serious Adverse Event

For this trial, an adverse event associated with the treatment or study procedure that suggests a significant hazard, contraindication, side effect or precaution (as described below) is to be reported as a serious adverse event (SAE). A serious adverse event (experience) or reaction is any untoward medical occurrence that:

- results in death,
- is life-threatening,
- requires inpatient hospitalization or prolongation of existing hospitalization,
- results in persistent or significant disability/incapacity, or
- is a congenital anomaly/birth defect.

Important medical events that may not result in death, be life threatening, or require hospitalization may be considered serious adverse events when, based upon appropriate medical judgment, they may jeopardize the patient and may require medical or surgical intervention to prevent one of the outcomes listed above.

8.1.3 Unexpected Adverse Event

An adverse event is considered unexpected when the nature (specificity) or severity of the event is not consistent with the risks described in the protocol or informed consent document for a particular protocol.

8.1.4 Grading Event Severity

This study has adopted usage of the National Cancer Institute (NCI) Common Technology Criteria for Adverse Events (CTCAE) version 4.0 and/or study-specific criteria for classification to describe the severity of adverse events with the exception of hyper and hypoglycemia. For this study, a reportable hypoglycemic event is defined as those resulting in loss of consciousness, seizure, or requiring assistance of others due to altered state of consciousness and hyperglycemic event is one resulting in DKA.

Adverse events will be graded on a scale from 1 to 5 according to the following standards in the NCI-CTCAE manual:

- Grade 1 = mild adverse event.
- Grade 2 = moderate adverse event.
- Grade 3 = severe and undesirable adverse event.
- Grade 4 = life-threatening or disabling adverse event.
- Grade 5 = death.

For additional information and a printable version of the NCI-CTCAE manual, go to <http://ctep.cancer.gov/reporting/ctc.html>

8.1.5 Attribution Definitions

Adverse events will be categorized for their relation to imatinib. The investigator will determine the relation, or attribution, of an AE to study participation and will record the determination on the appropriate CRF and/or SAE reporting form. The relation of an AE to study participation will be determined using definitions in Table 1.

Table 1. Attribution of adverse events

Code	Descriptor	Definition
Unrelated Category		
1	Unrelated	The adverse event is clearly not related.
Related Categories		
2	Unlikely	The adverse event is doubtfully related.
3	Possible	The adverse event may be related.
4	Probable	The adverse event is likely related.
5	Definite	The adverse event is clearly related.

8.2 ADVERSE EVENT REPORTING AND MONITORING

Study personnel will assess adverse events and the use of concomitant medications throughout the study. Adverse events will be reported to the Coordinating Center as described below. They will be graded as to severity according to common toxicity criteria or study-specific criteria and the investigator will make a determination as to the relation to therapy. Events will be assessed and reported in accordance with the ICH Guideline For Good Clinical Practice and per the guidance of the DHHS Office for Human Research Protections (OHRP). The adverse event case report form for the protocol must be completed for all adverse events (AE) of Grade 2 or greater severity regardless of relationship to therapy. For reporting serious adverse events (SAE), the MedWatch Form should also be completed and faxed to the Coordinating Center *within 24 hours of when the site was notified of the event*. This will be reviewed by the study Safety Monitoring Committee, and the Data and Safety Monitoring Board (DSMB) as appropriate. Deaths must be reported immediately. Event outcome and other follow-up information regarding the treatment and resolution of the event will be obtained and reported when available, if not known at the time the event is reported. The follow-up information should contain sufficient detail to allow for a complete medical assessment of the case and an independent determination of possible causality.

Adverse events will be assessed by the study designated Medical Monitor. The DSMB will conduct regular safety reviews approximately every three to six months (and, as needed) of adverse events by treatment group assignment. Serious adverse events as well as adverse events leading to treatment discontinuation will be reviewed by the DSMB.

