1.5.1.2 Gastrointestinal Reactions

Nausea constitutes the most common side effect of therapy. It has been noted in up to 40%–60% of subjects with CML or GIST, and it is usually mild, grade 1, and dose related. Nausea occurs much more commonly when the drug is taken on an empty stomach, and can be avoided when taken with food. Ingestion with food has not been shown to affect pharmacokinetic parameters. Diarrhea is also experienced by some patients, possibly from imatinib blockade of c-kit, and is often dose related.

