3.3.2 Secondary Endpoints

Efficacy:

1. MMTT-stimulated peak and 4 hour C-peptide AUC at weeks 52 and 104.
2. MMTT-stimulated 2 hour C-peptide AUC at week 104.
3. MMTT-stimulated 2-hour C-peptide AUC assessed longitudinally at weeks -2, 13, 26, 52, 78, and 104.
4. Insulin use in units per kilogram body weight per day at weeks 52 and 104.
5. Major hypoglycemic events, as defined in section 8.2.1, occurring from randomization at weeks 0, 52 and 104.
6. HbA1c levels at weeks 52 and 104.

Safety:

The rate of the following AEs in participants receiving imatinib or placebo:

1. Myelosuppression.
2. Gastrointestinal disorders.
3. Infections.
4. Hepatotoxicity.
5. Cardiac toxicity and edema.
6. Cutaneous reactions.
7. Muscle cramps, bone pain, arthralgias.
8. Fluid retention or peripheral edema.
9. Bone metabolism and growth abnormalities
10. Frequency and severity of all AEs in participants receiving imatinib or placebo.

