8. ADVERSE EVENTS

8.1 ADVERSE EVENT DEFINITION

8.1.1 Adverse Event

In this clinical trial, an adverse event is any occurrence or worsening of an undesirable or unintended sign, symptom or disease whether or not associated with the treatment and study procedures.

Throughout the study, the investigator must record all adverse events on source documents. Events not related to hypo or hyperglycemia that are Grade 2 or greater per the NCI CTCAE 4.0 (see Section 8.1.4. Grading Event Severity below) must be reported to the Coordinating Center on the appropriate adverse event form. The investigator should treat participants with adverse events appropriately and observe them at suitable intervals until the events resolve or stabilize.

Adverse events may be discovered through:

- observation of the participant;
- questioning the participant;
- unsolicited complaint by the participant

In questioning the participant the questioning should be conducted in an objective manner.

An abnormal value or result from a clinical or laboratory evaluation (e.g., a radiograph, an ultrasound, or an electrocardiogram) can also indicate an AE if it is determined by the investigator to be clinically significant. If this is the case, it must be recorded in the source document and as an AE on the appropriate AE form(s). The evaluation that produced the value or result should be repeated until that value or result returns to normal or can be explained and the participant's safety is not at risk.

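### The safety endpoints have no grade floor, but the AE form is required only from grade 2, so any-grade symptom rates and an all-AE rate cannot be obtained from the required forms

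*Combined protocol and SAP*

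**What the plan says.** All references are to the combined protocol and SAP.

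- **Endpoints.** Section 3.3.2 (and the Synopsis) introduces the safety endpoints as "The rate of the following AEs in participants receiving imatinib or placebo". Nine categories follow, then a tenth item: "Frequency and severity of all AEs in participants receiving imatinib or placebo". No item has a grade floor. Section 9.2 also lists the number and severity of adverse events among its secondary aims, again without a floor.
- **Definition.** Section 8.1.1 defines an adverse event without reference to severity, and Section 8.1.4 starts its grading scale at 1. A grade 1 event is therefore an adverse event of this study.
- **Data capture.** Section 8.2: "The adverse event case report form for the protocol must be completed for all adverse events (AE) of Grade 2 or greater severity". Section 8.1.1 gives the same threshold for what goes to the Coordinating Center: "Events not related to hypo or hyperglycemia that are Grade 2 or greater per the NCI CTCAE 4.0". For everything else the requirement is that "the investigator must record all adverse events on source documents". Clinically significant abnormal test results also go on the AE form, with no grade stated.
- **Expected severity.** Section 1.5.1.1 places the usual imatinib events in grades 1 to 2. Section 1.5.1.2 gives nausea in up to 40%–60% of oncology patients and says "it is usually mild, grade 1, and dose related". Sections 1.5.1.3 to 1.5.1.5 describe edema and arthralgia as mild to moderate and rash as usually grades 1–2.

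**The concern.** The endpoint list promises rates over all grades, while the data rule guarantees central data only from grade 2 upward. Nothing in Sections 3.3.2, 8 or 9 reconciles the two or provides for grade 1 events to be abstracted from site records. A report that followed the plan literally would tabulate grade 2 or higher symptom events under a heading that says all adverse events.

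This matters because low-grade tolerability is a real question here. Section 5.2 notes that side effects accepted in cancer care may be viewed differently in these participants. Section 3.6 expects effects to be milder and less frequent than in oncology, and milder effects would put more of the events below the reporting line.

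**Working it through.** The plan gives no figure that depends on this point, so there is nothing to reproduce. The check sets each endpoint against the data the plan requires.

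**Step 1. What can be computed from required data**

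| Endpoint (Section 3.3.2) | Grade 2 or higher | Any grade |
|---|---|---|
| 1 Myelosuppression | Yes, AE form | Yes, from hematology at every visit (Appendix 1), with neutrophil and platelet grade 1 ranges in Section 5.2.6 |
| 4 Hepatotoxicity | Yes, AE form | Yes, from the liver panel at every visit (Appendix 1), with grade 1 ranges in Section 5.2.5 |
| 9 Bone metabolism and growth | Yes, AE form | Largely, from scheduled calcium, phosphate, PTH, vitamin D and height |
| 2 Gastrointestinal, 3 Infections, 5 and 8 Edema and fluid retention, 6 Cutaneous, 7 Cramps, bone pain, arthralgia | Yes, AE form | No, grade 1 symptoms are required only in source documents |
| 10 All AEs | Yes, AE form | No, for the same reason |

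The only adverse-event rates for which Section 9.2 names a comparison model (Poisson regression) are those of severe events. These lie above the threshold and are untouched.

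**Step 2. Scale, using nausea as an illustration**

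Inputs from the documents: 66 participants (Synopsis) at 2:1 (Section 6.2.1), so 66 × 2/3 = 44 on imatinib and 22 on placebo; nausea in 40%–60% (Section 1.5.1.2, an oncology upper range). Assumption: the grade 1 share of nausea is not given; take 50% to 90%.

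- Participants with nausea = 44 × rate: 44 × 0.40 = 17.6 to 44 × 0.60 = 26.4.
- Grade 1 only, no form required = 44 × rate × share: 44 × 0.40 × 0.50 = 8.8 to 44 × 0.60 × 0.90 = 23.8.
- Left on required forms = 44 × rate × (1 − share): 44 × 0.40 × 0.10 = 1.8 to 44 × 0.60 × 0.50 = 13.2.

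**Step 3. Effect on a comparison, under assumed rates only**

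Assume any-grade rates of 50% on imatinib and 20% on placebo, and the same grade 1 share in both arms. Arcsine approximation, two-sided 0.05: power = Φ(h × √(44 × 22 / 66) − 1.96), with h = 2·asin√p₁ − 2·asin√p₀ and √(44 × 22 / 66) = 3.83.

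| Assumed grade 1 share | Rates counted | h | Power | Risk ratio | Risk difference |
|---|---|---|---|---|---|
| None removed | 50% vs 20% | 0.644 | 0.69 | 2.5 | 30 points |
| 50% | 25% vs 10% | 0.404 | 0.34 | 2.5 | 15 points |
| 80% | 10% vs 4% | 0.241 | 0.15 | 2.5 | 6 points |

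Under an equal share the ratio is unchanged; what shrinks is the absolute difference and the ability to see it. The plan does not power any such comparison, so these figures show direction and rough size only.

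**The case against.** The strongest reply is that the threshold is deliberate and harmless. It is stated twice, symptom dose-reduction rules in Section 5.2 generally begin at grade 2, and the rule applies equally to both blinded arms. It is also a mandatory minimum and does not forbid grade 1 entry. Section 8.1.5 records attribution on the CRF without a grade limit, Section 6.4 records concomitant medications with their indications, and source documents hold the rest.

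Much of this stands. A grade 2 threshold is a legitimate choice, and a comparison confined to grade 2 or higher is not biased by it. But optional entry would vary by site, and medication records would show only some treated events, so neither yields a defined all-grade rate. A deliberate threshold is a reason to align the endpoint wording with it.

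Four stronger readings are tempting, and the documents do not support them:

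- **That the expected effects are mostly grade 1.** This is said of nausea alone; the general statement is grades 1 to 2.
- **That the safety endpoints cannot be computed.** Grade 2 or higher rates, laboratory-derived rates and the severe-event analysis all can be.
- **That the rule worsens the unmasking problem in Section 3.6.** Whether side effects reveal assignment does not depend on whether they are entered on a form.
- **That a measurable loss of power has been shown.** The placebo rate and grade 1 share are assumptions. A different normal approximation, with placebo rates of 10% or 20% and shares of 50% to 90%, gave remaining power anywhere from about 6% to 51%.

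**Conclusion.** The mismatch is real and limited. For the symptom categories and for endpoint 10, the stated any-grade endpoint cannot be obtained from the AE forms that the plan requires. For blood counts and liver tests it can be derived from scheduled laboratory values, and it largely can for bone and growth.

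The consequence is an endpoint labelled more broadly than its data, and reduced sensitivity to low-grade effects that the protocol itself expects to be common. There is no bias in a grade 2 or higher comparison. The count of about 9 to 24 of 44 imatinib participants with grade 1 nausea only rests on an oncology rate, which may be high for this population, and on an assumed grade 1 share. The conclusion about the mismatch does not depend on that count. This should be corrected, but it threatens neither the primary analysis nor the severe-event analysis.

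**What to change.** Choose one of two routes and make Sections 3.3.2, 8.1.1, 8.2 and 9.2 and the Synopsis agree.

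1. **Restate the endpoints.** Define the symptom-category endpoints, endpoint 10 and the matching item in Section 9.2 as adverse events of CTCAE grade 2 or higher. Report any-grade myelosuppression and hepatotoxicity separately, derived from the scheduled laboratory values. The cost is a wording change and a short derivation rule.
2. **Collect grade 1 where it is wanted.** If any-grade rates are the aim, require grade 1 events in the listed symptom categories to be entered on the CRF at every site, from the source records that Section 8.1.1 already demands. The cost is modest extra data entry for about 66 participants, with no new assessments. If grade 1 entry is limited to those categories, endpoint 10 still needs a stated floor for all other events.

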8.2.1 Reporting Pregnancy

The investigator should be informed immediately of any pregnancy. At each visit the investigator will determine the pregnancy status of female participants and that the sexual partners of male participants. Pregnancy information should be entered into the electronic data capture (EDC) system within 24 hours of becoming aware of the event. The investigator should counsel the participant and discuss the risks of continuing with the pregnancy and the possible effects on the fetus. Monitoring of the participant should continue until the conclusion of the pregnancy. Follow-up information detailing the outcome of the pregnancy should be entered into the EDC system as it becomes available. Any premature termination of the pregnancy will be reported.

While pregnancy itself is not considered to be an AE or SAE, any pregnancy complication or elective termination of a pregnancy for medical reasons will be recorded as an AE or SAE as described in sections 8.2.1 and 8.2.2.

9. STATISTICAL CONSIDERATIONS AND ANALYSIS PLAN

Analyses of study data will be conducted to address the primary and secondary objectives of the trial, other stated objectives, and other interrelationships among elements of study data of interest to the investigators and of relevance to the objectives of the study. Such analyses may also entail the use of data from other studies in combination with data from this study. Likewise, data from this study may be used in combination with data from another study to address objectives of that study. Analyses by gender and race/ethnicity, as appropriate, are also planned.

9.1 PRIMARY OUTCOME AND ANALYSES

The primary outcome of each participant is the area under the stimulated C-peptide curve (AUC) over the first 2 hours of a 4-hour mixed meal glucose tolerance test conducted at the one-year visit. The AUC is computed using the trapezoidal rule that is a weighted sum of the C-peptide values over the 120 minutes. By the mean value theorem of integral calculus, the weighted mean C-peptide in pmol/mL is simply AUC/120.

The primary statistical hypothesis to be assessed in the study is whether:

- The mean C-peptide value for study subjects receiving imatinib is significantly higher than the mean value for placebo subjects.

The primary analysis will employ the weighted mean derived from the 2 hour AUC for each participant transformed as $\log(\text{mean C-peptide}+1)$. The comparison between the two treatment arms will be based on a t-test of treatment effect in an ANCOVA model adjusting for gender, baseline age and baseline $\log(\text{C-peptide}+1)$ ¹⁹⁰.

9.2 SECONDARY OUTCOMES AND ANALYSES

Additional analyses of the primary outcome will include:

- A log rank test of the difference in the hazard function between groups in the incidence of the loss of the 2 hour peak C-peptide < 0.2 pmol/ml on a semi-annual MMTT ¹⁹¹, and
- Longitudinal analyses using mixed effects models with a random intercept and slope of the C-peptide values over the post-treatment period, adjusted for the baseline level of C-peptide. The average intercept and slope will be compared between groups adjusting for age, gender and the baseline $\log(C\text{-peptide}+1)$.

Additional secondary objectives are to examine how imatinib affects the following:

- Mean area under the stimulated C-peptide curve (AUC) curve at 12 months
- Mean area under the stimulated C-peptide curve (AUC) over 4 hours at 24 months
- HbA1c levels over time
- Insulin dose (units/kg) over time
- Number of severe hypoglycemic events
- Number and severity of adverse events

The mean levels of quantitative variables (e.g. HbA1c and insulin dose) over all follow-up values will be compared between groups using a normal errors longitudinal analysis.

The prevalence of a binary characteristic (e.g. yes/no or positive/negative) at a single visit (e.g. a history of hypoglycemia during follow-up) will be assessed using a logistic regression model. The prevalence of a binary characteristic over time will be assessed using generalized estimating equations.

The rates of severe hypoglycemic events and severe adverse events will be computed (total number of events divided by total patient years of follow-up) and the rates compared using a Poisson regression model, allowing for over-dispersion using a quasi-likelihood model as appropriate. Tests of significance will employ a robust estimate of the variance.

The above analyses will also be conducted to adjust for age, gender, baseline $\log(C\text{-peptide}+1)$ and baseline HbA1c; and by race/ethnicity, as appropriate. Analyses will also be conducted to examine the effect of HLA or other genotype.

Analyses will also be conducted to assess heterogeneity of the effect of treatment group (the group difference) as a function of age, gender, baseline $\log(C\text{-peptide}+1)$ and baseline HbA1c; and by race/ethnicity and HLA or other genotype. Heterogeneity will

be assessed using a test of treatment group by covariate interaction in an appropriate regression model.

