3. STUDY DESIGN**3.1 DESCRIPTION**

The study will be a multicenter, two-arm, double-blind, placebo-controlled, 2:1 randomly assigned, phase II clinical trial for individuals with recent-onset T1DM. The randomly assigned participants will receive either a 6-month course of imatinib or matching placebo tablets over a period of 26 weeks. Both treatment and placebo groups will undergo identical procedures and will be followed for 104 weeks. The primary endpoint, 2-hour C-peptide AUC measured at 52 weeks in response to a mixed-meal tolerance test (MMTT), will be measured at 52 weeks. Safety, diabetes control, β -cell function, and immune function will be assessed for 104 weeks. Both groups will receive intensive diabetes management. During the follow-up phase, participants will undergo serial clinical and immunologic assessments over the 104 week study period, and possible mechanisms of imatinib action will be assessed.

Initial enrollment will be for subjects ages 18-45, with the goal to lower the age down to 12 upon acceptable safety review and prospect of benefit for this initial older cohort. When the first 10 enrollees have completed their week 26 assessment, the safety data will be reviewed by a subcommittee that includes the protocol chairs, the medical monitor, the clinical trial physician, and the DSMB. If the review concludes that significant safety concerns have been identified, then no further enrollment will occur pending further data review and evaluation by the DSMB. If the DSMB decides that the study may proceed then the FDA will be notified of study progress and determine if further age restriction is necessary, or if enrollment may be opened for subjects down to age 12. After the first 21 subjects have completed 6 months, a further safety review will occur for the DSMB. Additionally, an interim efficacy assessment will be conducted for the DSMB and FDA. The FDA will again be apprised of study progress, with further consideration for lowering the age of enrollees to 12, if this has not occurred earlier. If and when the age is lowered, an identical review procedure will be followed when the first 10 pediatric participants (ages 12-17) have completed their week 26 assessment. If the review is satisfactory, then enrollment will continue for subjects ages 12-45 until the study is fully enrolled.

[figure not shown]

Figure 3. Study Schema

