7.7 CHANGE IN BETA CELL FUNCTION

Many of the measures that we will utilize in assessing changes in beta cell function are now standard assessments in new-onset T1DM trials (see Section 3.3). However, these studies have ignored changes in insulin sensitivity. Imatinib may have novel effects on beta cell function and insulin sensitivity, as noted by the pre-clinical studies and effects in subjects with type 2 diabetes. We recognize that euglycemic hyperinsulinemic clamps are the gold standard for assessment of insulin sensitivity, but pose significant additional subject and investigative team burden and expense. We will assess changes in adiponectin levels in study patients, as these have shown dramatic increases in patients with type 2 DM on imatinib¹²⁶. We will also use data derived from MMTTs to model beta cell function and insulin sensitivity, as has been employed by others^{181,182}(see letter of collaboration from [name]). In addition to glucose and c-peptide levels, plasma glucagon, and proinsulin levels will be measured to further explore the effects of Imatinib on insulin sensitivity.

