Appendix 1. Schedule of Events

Week	-3 to -4	0	2	4	9	13	17	22	26	39	52	78	104
Visit	-1	0	1	2	3	4	5	6	7	8	9	10	11
GENERAL ASSESSMENTS													
Informed consent	X												
Eligibility criteria	X												
Medical history	X												
Adverse events	X	X	X	X	X	X	X	X	X	X	X	X	X
Concomitant medications	X	X	X	X	X	X	X	X	X	X	X	X	X
Physical examination ¹	X	X		X	X	X			X		X	X	X
Secondary sexual characteristics ²		X									(X)		(X)
Vital Signs	X	X	X	X	X	X	X	X	X	X	X	X	X
Pregnancy Monitoring (if applicable)	X	X		X	X	X	X	X	X		X	X	X
ECG	X		X										
LABORATORY ASSESSMENTS													
Serum chemistries and liver panel ³	X	X	X	X	X	X	X	X	X	X	X	X	X
Autoantibodies	X												
Hematology ⁴	X	X	X	X	X	X	X	X	X	X	X	X	X
Infectious disease serology ⁵	X												
PPD skin test or IGRA	X												
Urine hCG	X	X		X	X	X	X	X	X		X	X	X
Urinalysis	X								X		X		X
Prostate Specific Antigen (males only)		X							X		X		X
C-peptide levels (tested from MMTT) ⁶	X					X			X		X	X	X

¹Excluding genitalia unless clinically indicated

² The Tanner stages will be assessed at the baseline visit for every participant under 18 years of age. After the baseline visit, Tanner stages will be assessed annually on all participants who are < stage 3. If the Tanner stage is ≥ 3 at the baseline visit or any subsequent visit, Tanner stages will not need to be assessed at any future visit.

³ To include sodium, calcium, potassium, chloride, phosphate, total CO₂, BUN, creatinine, AST, ALT, alkaline phosphate, direct and total bilirubin.

⁴ Performed locally; to include CBC with differential and platelets.

⁵ Hepatitis B and C, HIV, toxoplasmosis, VZV, EBV, and CMV serology. CMV/EBV PCR testing may be obtained (centrally) or locally, if necessary to confirm active infection.

⁶ 4-hour MMTT at Visits -1, 9, 11 and 2-hour MMTT at Visits 4, 7, and 10.

Week	-3 to -4	0	2	4	9	13	17	22	26	39	52	78	104
Visit	-1	0	1	2	3	4	5	6	7	8	9	10	11
Plasma Glucose (tested from MMTT) ⁵	X					X			X		X	X	X
HbA _{1c} levels	X					X			X	X	X	X	X
STUDY DRUG ADMINISTRATION													
Study drug administration		X	X	X	X	X	X	X	X				
Study drug compliance			X	X	X	X	X	X	X				
DISEASE SPECIFIC ASSESSMENTS													
Glucose (Glucometer Reading)		X	X	X	X	X	X	X	X	X	X	X	X
Insulin use		X	X	X	X	X	X	X	X	X	X	X	X
Hypoglycemia assessment		X	X	X	X	X	X	X	X	X	X	X	X
Serum-Adiponectin ⁷		X		X					X		X		X
Plasma-Glucagon ⁶	X					X			X		X	X	X
Plasma-Proinsulin ⁶	X					X			X		X	X	X
BONE AND MINERAL METABOLISM													

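### Insulin use and HbA1c are endpoints at weeks 52 and 104, but section 9.2 tests only their mean over all follow-up and gives no contrast at either week

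*Combined protocol and SAP*

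**What the plan says.** Section 3.3.2 (and the synopsis) lists, as efficacy endpoint 4, "Insulin use in units per kilogram body weight per day at weeks 52 and 104" and, as endpoint 6, "HbA1c levels at weeks 52 and 104".

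Section 9.2 restates the insulin item as "Insulin dose (units/kg) over time", and words HbA1c in the same way. Its method for such variables is: "The mean levels of quantitative variables (e.g. HbA1c and insulin dose) over all follow-up values will be compared between groups using a normal errors longitudinal" model. The single-visit method in 9.2 (logistic regression) is for binary characteristics. The C-peptide mixed model in the same section is limited to the period after treatment; the insulin and HbA1c comparison carries no such limit.

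Treatment is "a 6-month course of imatinib or matching placebo tablets over a period of 26 weeks" (section 3.1). Appendix 1 schedules insulin use at every visit from week 0 to week 104, and HbA1c at screening and then at weeks 13, 26, 39, 52, 78 and 104. Section 7.7 states: "Imatinib may have novel effects on beta cell function and insulin sensitivity".

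**The concern.** The endpoint asks whether the arms differ at two named times, both well after drug has stopped. The planned test asks whether they differ on average over the two years, including the time on drug. The two answers can diverge.

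Section 1.4.2 reports raised adiponectin and better glycaemic control during imatinib treatment in people with type 2 diabetes, and section 7.7 raises an effect on insulin sensitivity. If insulin need fell only while drug was taken, the averaged mean would move although nothing differed at weeks 52 or 104. Conversely, a difference that appeared only late would be averaged with earlier visits that show none.

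These are two of the six secondary efficacy endpoints, and section 2.2 makes lasting efficacy a secondary objective. With no visit contrast named in advance, the choice of which result represents the endpoint could also be made after the data are seen.

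**Working it through.** **Visit counts (Appendix 1, post-baseline)**

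| | Follow-up visits (weeks) | Through week 26 | Weeks 52 and 104 |
|---|---|---|---|
| Insulin use | 2, 4, 9, 13, 17, 22, 26, 39, 52, 78, 104 | 7 of 11 (64%) | 2 of 11 (18%) |
| HbA1c | 13, 26, 39, 52, 78, 104 | 2 of 6 (33%) | 2 of 6 (33%) |

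If week 26 is not counted as on drug, the insulin figure is 6 of 11 (55%).

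**The plan's own figure.** The plan gives no power for insulin or HbA1c. For the primary outcome, section 9.4 gives 40 versus 20 participants, means 0.306 and 0.445, RMSE 0.185, one-sided 0.05 and 85% power. The standardised difference is 0.139/0.185 = 0.751. The noncentrality is 0.751/√(1/40 + 1/20) = 0.751/√0.075 = 2.74. With 58 df, power is 0.857, which reproduces the 85%. I use the same sample size below, with 0.75 SD as a yardstick only.

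**Assumptions not in the documents.** Unit SD at each visit, complete data, no baseline covariate, and two-sided 0.05 (9.2 sets no level or sidedness for secondary tests). Two covariance families, because the plan states none:

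- Exchangeable, correlation ρ from 0.4 to 0.8. Every visit has equal weight, and the variance of a person's mean over k visits is v = [1 + (k − 1)ρ]/k.
- Decaying, correlation r per 13 weeks with r from 0.7 to 0.9. Generalised least squares (GLS) weights are w = V⁻¹1/(1ᵀV⁻¹1), and v = 1/(1ᵀV⁻¹1).

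In both, noncentrality = d × (total weight on visits with an effect)/√(0.075v), with 58 df and critical value 2.002.

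**Worked case: insulin, ρ = 0.6.** v = (1 + 10 × 0.6)/11 = 0.636, and √(0.075 × 0.636) = 0.218.

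- On-drug-only effect, d = 0.5: mean effect 0.5 × 7/11 = 0.318; noncentrality 1.46; rejection 30%.
- Effect only from week 52 on, d = 0.75: mean effect 0.75 × 3/11 = 0.205; noncentrality 0.94; power 15%.
- Effect at every visit, d = 0.75: noncentrality 3.43; power 92%.

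**Worked case: HbA1c, ρ = 0.6.** v = (1 + 5 × 0.6)/6 = 0.667, and √(0.075 × 0.667) = 0.224.

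- On-drug-only, d = 0.5: 0.5 × 2/6 = 0.167; noncentrality 0.75; rejection 11%.
- From week 52 on, d = 0.75: 0.75 × 3/6 = 0.375; noncentrality 1.68; power 38%.

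**Ranges**

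| True effect | Insulin, exchangeable | Insulin, decaying | HbA1c, exchangeable | HbA1c, decaying | Week-52 contrast |
|---|---|---|---|---|---|
| 0.5 SD, on drug only | 24–40% | 16–19% | 10–14% | 14–15% | 5% |
| 0.75 SD, from week 52 on | 13–19% | 39–61% | 31–48% | 40–63% | 77% |
| 0.75 SD, every visit | 84–98% | 89–99% | 84–97% | 88–98% | 77% |

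Under decaying correlation the on-drug visits carry 39–44% of the insulin weight, not 64%. Counting week 26 as off drug lowers the first insulin cell to 19–31%.

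**The case against.** A reader might infer that the averaged test would miss a durable benefit. It would not: an effect of 0.75 SD at every visit has 84–99% power under the average, against 77% at one visit. One that builds linearly over 26 weeks and then persists keeps 54–87% for insulin and 72–94% for HbA1c. Clear loss needs later emergence; a 52-week build-up gives 32–78% for insulin. The plan itself assumes a C-peptide effect at about six months (section 9.5).

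A reader might also infer that the protocol expects an insulin-sensitising effect. It says only that one may occur, and the clinical evidence in 1.4.2 is mostly case reports and small series in type 2 diabetes. No on-drug effect size for insulin dose is given.

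Nor is the average necessarily dominated by on-drug data. That holds for the insulin visit count, but not for the weights under decaying correlation, and not for HbA1c. Treat-to-target management in both arms (sections 3.6 and 6.1) also makes a large HbA1c difference less likely.

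Finally, an on-drug effect has interest of its own: section 2.2 includes insulin sensitivity, and the wording of 9.2 about levels over time suits an average. Section 3.3.3 adds binary insulin and HbA1c outcomes at weeks 52 and 104.

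These points limit the size and wording of the concern. They do not supply the missing test: the 3.3.3 outcomes are exploratory and dichotomised, and the continuous endpoints in 3.3.2 still have no contrast at their stated weeks.

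**Conclusion.** The mismatch between 3.3.2 and 9.2 is real and rests on the text and visit schedule alone. For insulin, the averaged test can respond to an effect confined to the drug period and can dilute one that emerges late. For HbA1c the issue is mainly dilution.

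The size is illustrative. With 40 versus 20, unit SD and two-sided 0.05, an on-drug-only effect of 0.5 SD is declared 16–40% of the time for insulin and 10–15% for HbA1c, against 5% for a week-52 contrast. A 0.75 SD effect present only from week 52 on has 13–61% power for insulin and 31–63% for HbA1c, against 77%. The width of these ranges reflects a covariance structure that the plan leaves open. The primary analysis is unaffected. The point should be corrected, but it does not threaten the trial's main conclusion.

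**What to change.** In section 9.2, fit the longitudinal model for insulin dose and for HbA1c with visit as a categorical factor and treatment-by-visit terms, adjusted for the baseline value. Name the between-arm contrasts at week 52 and week 104 as the tests of endpoints 4 and 6, and state the covariance structure. Keep the all-follow-up mean as a supportive result, reported separately through week 26 and after week 26.

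The cost is wording only: every measurement is already in Appendix 1. The downside is some loss of precision if the effect is constant over time (77% at one visit against 84–99% for the average in the illustration). The supportive mean retains that information.
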